8.1 Screening

Subjects will be screened at the Screening Visit (Visit 1), and eligible subjects will be enrolled into the observational period of the study.

Re-screening of subjects who fail entry criteria for any reason is permitted only under select circumstances as outlined below.

- Screen failure due to stabilization timeframes: If it is determined prior to the completion of Screening Visit that the subject did not meet eligibility pertaining to any of the following:
 - < 4 months since the surgical procedure (Inclusion #2a),
 

 - O Timeframe required for stabilization of chronic medications or medical history (Exclusion #1a, 2, 3, 4, 6, 7, 8, 9, 10, 11, 17, 20a), or
 - O Time window required for ocular medication or pain medication use prior to the screening visit (Exclusion #2),

the subject will be screen failed and may be brought back at a later date after the proper timeframes have been achieved to re-attempt the screening process.

- Screen failure under protocol version 02 due to ocular pain severity eligibility criteria that would have been met under protocol version 03: If a subject was screen failed under protocol version 02 due to the following pain severity inclusion criteria:
 - Ocular pain severity VAS < 50 mm at Screening Visit (per Inclusion #3)
 - the subject may be brought back at a later date to re-attempt the screening process.
- Screen failure due to insufficient reduction in ocular pain during the anesthetic test caused by technologic or procedural issues: If a subject was screen failed due to an insufficient ocular pain reduction during the anesthetic test, the subject may be allowed to re-screen in specific circumstances (including device malfunction, procedural errors). In all cases, the site must receive Sponsor approval prior to re-screening.

In the case of re-screening, the subject will receive a new subject number and all screening assessments required at Screening Visit must be completed, regardless whether the assessments were conducted at the previous screening visit.

Re-screening is only allowed one time for each subject, with the exception of subjects who screen failed due to pain severity eligibility criteria under protocol version 02. A subject who screen failed under this criterion potentially could be re-screened a second time based on the additional re-screening criteria stated above. Re-screening must not be used as a method to force subject eligibility into the study.

8.1.1 Information to be collected on screening failures

Subjects who sign an informed consent form and are subsequently found to be ineligible prior to randomization will be considered a screen failure. The reason for screen failure should be recorded on the appropriate eCRF. The informed consent, demographic information, and Inclusion/Exclusion pages must also be completed for screen failure subjects. No other data

will be entered into the clinical database for subjects who are screen failures, unless the subject experienced a serious adverse event (SAE) during the screening phase (see 10.1.2 SAE section for reporting details). If the subject fails to be randomized, the IRT must be notified within 2 days of the screen fail that the subject was not randomized.

Subjects who are randomized and fail to start treatment, e.g. subjects randomized in error, will be considered an early terminator. The reason for early termination should be recorded on the appropriate eCRF.

8.2 Subject demographics/other baseline characteristics

The following information will be collected/documented at Screening/Baseline Visits for each randomized subject:

- Age
- Sex
- Race/Ethnicity
- Ancestry (applicable for Japanese and Chinese only)
- Iris color

Ocular baseline characteristic will include:

- Time since date of the last surgery
- Surgery type (PRK,LASIK, LASEK, RK, SMILE or Cataract)
- Pain Characterization Questionnaire
- Frequency of artificial tear use
- Frequency of rescue medication use
- Corneal fluorescein staining
- Conjunctival lissamine staining
- Conjunctival redness score
- Schirmer score

Baseline values of efficacy parameters:

- Pain Severity VAS
- Pain frequency VAS
- OPAS

8.3 Efficacy

8.3.1 Pain Severity and Frequency Visual Analog Scales

The pain severity Visual Analogue Scale (VAS) is to be completed through an electronic diary by the subject at the Screening Visit, and thereafter every evening (before bed during the observational period, and before their evening dose of study medication during the study treatment period). The subject will provide a score for severity of their ocular pain over the past 24 hours by putting a vertical mark on the horizontal scoring line. The severity scoring line utilizes the anchors of 'No Pain' to 'Very Severe' pain.

The Pain Frequency Visual Analogue Scale (VAS) is to be completed through an electronic diary by the subject at the Screening Visit, and thereafter every evening (before bed during the observational period, and before their evening dose of study medication during the study treatment period). The subject will provide a score for frequency of their ocular pain over the past 24 hours by putting a vertical mark on the horizontal scoring line. The frequency scoring line utilizes the anchors of 'Rarely' to 'All the Time'.

8.3.2 OPAS questionnaire

The Ocular Pain Assessment Survey (OPAS) questionnaire is completed electronically by the subject at each office visit as indicated in the Schedule of Assessments. The OPAS will be used to assess the subject's ocular pain, aggravating factors, quality of life, and perception of overall improvement of ocular and non-ocular pain. The OPAS is a multidimensional tool specifically designed to assess ocular pain in subjects with eye pain of any origin.

8.3.4 Appropriateness of efficacy assessments

The efficacy assessments included in this study for the evaluation of ocular pain are commonly used in clinical research.

8.4 Safety

Safety assessments are specified below and the assessment schedule details when each assessment is to be performed. If the COVID-19 pandemic limits or prevents on-site study visits, phone calls or virtual contacts should be conducted for safety monitoring and discussion of the subject's health status, until the subject can again visit the site.

Clinically significant abnormalities, per the opinion of the Investigator, for any of the safety parameters will be recorded on the ocular medical history page of the eCRF if present at the time of informed consent, and on the AE page if occurring on or after the time of consent.

For details on AE collection and reporting, refer to Section 10.1 - Definition of adverse events and reporting requirements

8.4.1 Laboratory evaluations

Not Applicable

8.4.2 Pregnancy

Women of child bearing potential must be informed that taking the study treatment may involve unknown risks to the fetus if pregnancy were to occur during the study, and must agree that in order to participate in the study they must adhere to the contraception requirements outlined in the exclusion criteria.

All women of childbearing potential who are not surgically sterile will have a urine pregnancy test. These assessment results must be captured in the source documentation. Additional urine pregnancy tests may be performed at the discretion of the investigator and/or according to local requirements and the test results will be recorded in the source document. A positive urine pregnancy test requires immediate interruption of study drug until serum beta-human chorionic gonadotropin (B-hCG) is performed and found to be negative. If positive, the subject must be discontinued from the trial.

8.4.3 Visual Acuity

Visual acuity (VA) will be performed using a Snellen chart. VA testing should precede IOP measurement, the administration of eye drops to dilate or anesthetize the eye, or any examination requiring contact with the eye.

8.4.4 Slit Lamp Examination

At every scheduled visit, the anterior segment's structures of the study eye will be carefully examined according to clinical practice. The slit lamp results will be recorded in the source documents.

8.4.5 Intraocular Pressure

Intraocular pressure (IOP) will be measured according to the standard clinical practice and expressed in mmHg. Every effort should be made to use the same method/instrument throughout the study.

If using Goldmann applination tonometry, the IOP measurement should be performed after the corneal fluorescein staining and lissamine conjunctival staining at Visit 2 and Visit 6, to avoid the staining outcomes are confounded by the anesthetic.

8.4.6 Dilated Fundus Exam

For the fundus exam pupil must be dilated. Fundus results will be recorded in the source documents

8.4.7 Corneal Endothelial Cell Microscopy

Each site must use the specified brand of equipment for use on all subjects at the site. Certification of the equipment and examiners at each investigative site will occur prior to evaluation of study subjects. At the Baseline and End of Treatment Visits Specular microscopy of the corneal endothelial cell images will be obtained by the Investigator and submitted to the Central Reading Center (CRC) to determine the changes in endothelial cell count, density, and shape from the initial baseline to the end of treatment. A standardized procedure for the collection of the Specular microscopy images will be provided by the CRC in a separate manual.

8.4.8 Appropriateness of safety measurements

The safety assessments selected are standard for this indication/subject population.

8.5 Additional assessments

8.5.1 Other Assessments

In vivo confocal microscopy is included as an exploratory assessment at select sites to evaluate corneal nerve morphology in patients with CICP.

The following ocular surface assessments (corneal and conjunctival staining, conjunctival redness, Schirmer's test) are included to evaluate whether long term inhibition of TRPV1 receptors with SAF312 eye drops has an adverse effect on ocular surface parameters.

Finally, the Pain Characterization questionnaire will be used to gain greater detail regarding the subject's ocular pain.

Frequency of artificial tear/gel/lubricant use and rescue medication use will be captured in the eDiary on a daily basis to gain insights to subject behavior with these products.

[figure not shown]
8.5.1.1 In Vivo Confocal Microscopy

In Vivo Confocal Microscopy (IVCM) will be performed by the Investigators only at selected sites for exploratory analysis. The images will be sent to an independent reader for objective and subjective evaluation to quantify and evaluate the distribution and morphology of corneal nerves. A standardized procedure for the collection of the images will be provided in a separate manual.

8.5.1.2 Conjunctival Redness

Redness of the interpalpebral conjunctiva will be evaluated by the investigator using the McMonnies scale (Figure 8-1). The inter-palpebral region of the temporal and nasal regions will each be graded using the 0-5 scale.

Figure 8-1 McMonnies Redness Photographic Scale

8.5.1.3 Corneal Fluorescein Staining

[figure not shown]
Corneal fluorescein staining will be conducted by the Investigator. For individual subjects, corneal fluorescein staining should be assessed by the same examiner at all visits using the same slit lamp and the same settings.

Fluorescein impregnated strips (to be provided by Novartis) will be used to deliver dye to the ocular surface. To wet the strip, a single drop of sterile saline solution (or similar) is placed on the tip of the strip. Anesthetic drops must NOT be used as a wetting agent.

Immediately after application of the wetting drop, the strip should be gently flicked to remove excess fluid. Immediately after flicking the strip, the wet tip of the strip is allowed to gently touch the inner edge of the inferior cul-de-sac of the eye to draw the fluorescein onto the ocular surface. The subject should be instructed to not rub their eyes and gently blink several times to distribute the dye across the ocular surface.

The degree of staining is based on the Corneal Fluorescein Modified NEI Scale. Each of the five regions (as depicted in the diagram, and defined as central (C), superior (S), inferior (I), temporal (T), and nasal (N)) will be graded based on a scale of 0 to 4, with higher scores suggestive of higher degrees of corneal staining (Figure 8-2). The examiner will indicate the appropriate score for each region. If the assessment falls between grades, round up to the higher score. After entry of the scores per region, the total or composite (sum) score for each eye will be automatically calculated (maximum score = 20/eye).

Figure 8-2 Corneal Fluorescein Modified NEI Scale

Grade 0	No staining
Grade 1	Superficial micropunctate staining covering < 25% of the corneal surface
Grade 2	Macropunctate staining AND/OR superficial micropunctate staining covering 25-50% of the corneal surface
Grade 3	Some coalesced macropunctate staining AND/OR superficial micropunctate staining covering 51-75% of the corneal surface
Grade 4	Numerous coalesced macropunctate areas and/or patches AND/OR superficial micropunctate staining covering > 75% of the corneal surface

8.5.1.4 Conjunctival Lissamine Staining

Conjunctival lissamine staining will be conducted by the Investigator and after corneal fluorescein staining. For individual subjects, conjunctival lissamine staining should be assessed by the same examiner at all visits using the same slit lamp and the same settings.

Lissamine impregnated strips (to be provided by Novartis) will be used to deliver the dye to the ocular surface. To wet the strip, a single drop of sterile saline solution (or similar) is placed on the tip of the strip. Anesthetic drops must NOT be used as a wetting agent.

Immediately after application of the wetting drop, the strip should be gently flicked to remove excess fluid. Immediately after flicking the strip, the wet tip of the strip is allowed to gently touch the inner edge of the inferior cul-de-sac of the eye to draw the lissamine onto the ocular surface. The subject should be instructed to not rub their eyes and gently blink several times to distribute the dye across the ocular surface.

The degree of lissamine staining in the temporal and nasal inter-palpebral conjunctiva will be assessed based on the proportion of the area that is covered by staining. The proportion of staining area will be assessed based on the table provided in Table 8-3:

Table 8-3 Grading of Conjunctival Staining

Grading scale	Percentage of the staining area		
0	0%		
1	1%–15%		
2	16%–30%		
3	31%–45%		
4	>45%		

The score for nasal and temporal regions will be captured separately and the total conjunctival lissamine staining will be the sum of the nasal and temporal scores (total score of 0-8).

8.5.1.5 Schirmer's Test (without anesthesia)

The Schirmer's test will be performed without anesthetic in both eyes simultaneously, and after completion of ocular surface stainings.

The subject should be seated in the examining chair with the room lights dimmed and their head against a headrest for comfort. Prepare the sterile strips (Tear FloTM or similar) while they are still in the package by folding the rounded end at the indentation (approximately 5 mm from the tip). The strip will be bent and inserted between the bulbar and palpebral conjunctiva over the inferior lid margin in the lateral third of the eyelid towards the lateral canthus, and left in place for 5 minutes with the eyes closed. Tear secretion is measured in millimeters of the length of strip wetted by tears. The measurement (score) will be made to the nearest whole number.

8.5.1.6 Mitigation of Placebo Response Training Video and Pain Assessment Knowledge Check

At Screening Visit (Visit 1): Upon completion of ICF but before starting the use of ePRO device, the subject will use the study tablet device, personal mobile device, laptop, or tablet to watch a video regarding placebo response mitigation.

After completing the video, a printed copy of the Pain Assessment Knowledge Check will be given to the subject to have him/her complete the questions in order to check their level of

understanding of the video content. Site staff should review the responses with the subject and answer any questions they may have regarding incorrect responses or the information as a whole.

At Baseline/Randomization Visit (Visit 2): if the subject meets criteria for randomization, the study subject is expected to watch the Video once more BEFORE they leave the clinic. The Pain Assessment Knowledge Check can be optional for any subject who had completed the Knowledge Check already during Visit 1 (Screening).

8.5.1.7 Pain Characterization Questionnaire

The Pain Characterization questionnaire is a series of questions asking about the specific details of the subject's ocular pain (e.g., pain descriptors, timing throughout the day) that is not already captured in the other questionnaires included in the efficacy assessments. The pain characterization questionnaire will be collected electronically at Screening Visit only and therefore not intended for any safety or efficacy assessments.

8.5.1.8 Post-Anesthetic Severity of Eye Pain

The anesthetic test will be administered to identify subjects with primarily peripheral neuropathic pain.

The subject will be asked to complete the pre-anesthetic pain severity VAS question in the ePRO. After the subject records the pain severity score, one drop of topical ocular anesthetic will be administered in each eye per the study site standard practice (e.g., Tetracaine, proparacaine). Once the anesthetic has taken effect, within 5 min of drop instillation, the subject will complete the post-anesthetic severity eye pain VAS question in the ePRO. For both the pre-and post-anesthetic pain severity, the subject will complete the pain severity VAS considering the pain at the time when each question is completed. The question is the same pain severity question as described in Section 8.3.1., with the severity scoring line anchors of 'No Pain' to 'Very Severe' pain.

The ePRO will calculate the difference between the pre-anesthetic pain severity score and the post-anesthetic score (must be $\geq 60\%$ for subject to qualify for the study).

9 Discontinuation and completion

9.1 Discontinuation

9.1.1 Discontinuation of study treatment

Discontinuation of study treatment for a subject occurs when study treatment is permanently stopped for any reason (prior to the planned completion of study drug administration, if any) and can be initiated by either the subject or the investigator.

The investigator must discontinue study treatment for a given subject if, he/she believes that continuation would negatively impact the subject's well-being.

Discontinuation from study treatment is required under the following circumstances:

- Subject decision
- Pregnancy
- Use of prohibited treatment as per recommendations in the prohibited treatment (Section 6.2.2)
- Any situation in which continued study participation might result in a safety risk to the subject
- Following emergency unblinding
- Adverse events
- Unsatisfactory therapeutic effect

If discontinuation from study treatment occurs, the investigator should make a reasonable effort to understand the primary reason for the subject's discontinuation from study treatment and record this information.

Subjects who discontinue from study treatment agree to return for the end of treatment and follow-up visits indicated in the Assessment Schedule (refer to Section 8).

If the subject cannot or is unwilling to attend any visit(s), the site staff should maintain regular telephone contact with the subject, or with a person pre-designated by the subject. This telephone contact should preferably be done according to the study visit schedule.

After discontinuation from study treatment, at a minimum, in abbreviated visits, the following data should be collected at clinic visits or via telephone/email contact:

- New / concomitant treatments
- AE / SAE

The investigator must also contact the IRT to register the subject's discontinuation from study treatment.

If discontinuation occurs because treatment code has been broken, please refer to Emergency breaking of treatment code in Section 6.6.3.

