Part	A single component of a study which contains different objectives or populations within that single study. Common parts within a study are: a single dose part and a multiple dose part, or a part in patients with established disease and in those with newly-diagnosed disease.
Patient	An individual with the condition of interest
Period	A minor subdivision of the study timeline; divides phases into smaller functional segments such as screening, baseline, titration, washout, etc.
Randomization number	A unique identifier assigned to each randomized subject, corresponding to a specific treatment arm assignment
Screen Failure	A subject who is screened but is not treated or randomized
Study completion	Point/time at which the subject came in for a final evaluation visit or when study drug was discontinued whichever is later.
Study drug/treatment	Any drug (or combination of drugs) administered to the subject as part of the required study procedures; includes investigational drug, active drug run-ins or background therapy.
Discontinuation from study	Point/time when the participant permanently stops receiving the study treatment and further protocol required assessments or follow-up, for any reason. No specific request is made to stop the use of their samples or data.
Discontinuation from study treatment	Point/time when the participant permanently stops receiving the study treatment for any reason (prior to the planned completion of study drug

	administration, if any). Participant agrees to the other protocol required assessments including follow-up. No specific request is made to stop the use of their samples or data.
Subject	An individual who has consented to participate in this study. The term Subject may be used to describe either a healthy volunteer or a patient.
Subject number	A number assigned to each subject who enrolls in the study. When combined with the center number, a unique identifier is created for each subject in the study.
Variable	A measured value or assessed response that is determined in specific assessments and used in data analysis to evaluate the drug being tested in the study
Vehicle	A vehicle refers to the inactive version of the investigational medicinal product (IMP) i.e., it contains all the components of the IMP with the exception of the drug (active ingredient). In this protocol, the term placebo may be used interchangeably with vehicle as the placebo also does not contain any drug (active ingredient).

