2.2 Secondary Estimands

Not applicable.

3 Study design

Figure 3-1 Study Design

This study is a Phase 2 randomized, double-blinded, multi-center, parallel group, placebo-controlled evaluation of the safety and efficacy of SAF312, 5 mg/ml and 15 mg/ml eye drops versus placebo used twice-daily in both eyes for 12 weeks. Eligible subjects will have undergone refractive surgery (i.e., PRK, LASIK, LASEK, RK, or SMILE) in both eyes or cataract surgery in both eyes, with or without refractive enhancement in one or both eyes at least 4 months prior to Screening, and have been suffering from chronic ocular pain as a result of the their surgery. Both eyes do not necessarily need to have undergone surgery on the same day. If the second eye underwent surgery on a different day than the first, eligibility for time since surgery would be based on the date of the most recent surgery. In cases where more than one procedure was performed on an eye (eg, refractive surgery with CICP followed some time later by cataract surgery, or cataract surgery followed some time later by refractive enhancement), the Screening visit must be \geq 4 months after the most recent procedure. Eligible patients must also demonstrate chronicity of the pain as described in inclusion criteria. Overall approximately 150 subjects will be enrolled in the study (i.e. approximately 50 subjects will be enrolled in each treatment arm in 1:1:1 ratio).

The study will consist of a 12 week observation period starting from Screening Visit (Visit 1) until the Baseline/Randomization Visit (Visit 2). Subjects who qualify for randomization will then be asked to attend visits every two weeks for the first 4 weeks, and then monthly for the remainder of the 12 week treatment period. End of Treatment (EOT) will occur at Visit 6 when the subject receives the last study treatment. End of Study (EOS) will occur 4 days after EOT.

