Medical history / current medical conditions	X								
Previous /Con Meds	Х	Х	Х		Х	Х	Х	Х	Х
Inclusion / Exclusion criteria	Х		Х						
Pregnancy test (dipstick/strip)			S					S	
Adverse Events	Х	Х	Х		Х	Х	Х	Х	Х
Anesthetic test	Х								
Placebo response mitigation training video and knowledge check	S			S ¹					
Dispense electronic diary	S								
Pain Severity VAS	X ²	R	\mathbb{R}^3	R⁴	R^4	R^4	R ⁴		
Pain Frequency VAS	X ²	R		R ⁴	R^4	R ⁴	R ⁴		
Artificial tears use	X ²	R		R⁴	R ⁴	R ⁴	R ⁴		
Rescue medications	X ²	R		R ⁴	R ⁴	R^4	R ⁴		
OPAS Questionnaire	Х		X ⁶		X ⁶	X ⁶	X ⁶	X ⁶	
Pain Characterization Questionnaire	Х								

Period	Screening		Treatment				Post Treatment Follow-up		
Visit Name	Visit 1 Screening	Phone Check-in	Visit 2 Baseline	Visit 2 Randomization	Visit 3	Visit 4	Visit 5	Visit 6 / EOT	Follow-up Contact / EOS
Days	-84	-42 ± 7	1	1	14 ± 2	28 ± 2	56 ± 2	84 ± 2	EOT + 4
Visual Acuity	Χ		X					X	
Slit lamp examination	Х		X		Х	Х	Х	Х	
Signs evaluation: (Corneal fluorescein staining; Conjunctival lissamine staining. Conjunctival redness; Schirmer score)	X		х		Х	х	х	х	
Contact IRT	Х			Х	Х	Х	Х	Х	
Intraocular Pressure (IOP)			Х					Х	
Ophthalmoscopy dilated fundus exam			Х					Х	
Corneal endothelial cell microscopy			Х					Х	
In vivo confocal microscopy ⁷			X					X	
Dispense study medication				S ⁸	S	S	S		
Collect electronic diary								S	
Collect study medication					S	S	S	S	
Electronic diary compliance check ⁹			S		S	S	S	S	

^X Assessment to be recorded in the clinical database or received electronically from a vendor

S Assessment to be recorded in the source documentation only

Reminder for the tasks to be completed by the subject outside of the clinical site

¹ The Pain Assessment Knowledge Check can be optional for any subject who had completed the Knowledge Check already during Screening Visit (Visit 1).

² Two entries to be completed on the same day of screening. The first entry is to be made at the time of the on-site screening visit, the second entry and all subsequent entries are to be completed at home before their evening dose of study medication.

³ Confirm eligibility based on the eDiary data.

⁴ Remind the subject to complete the once daily eDiary recording prior to the evening dose of study medication every day until the evening prior to the EOT visit.

⁶ Enter the PIN code and select the scheduled visit on the Visit Selection menu to allow the study subject to complete the questionnaire on the tablet device

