12.4.6 Supplementary analysis

A supplementary clinical question of interest is: What is the effect of SAF312 versus placebo on change from baseline in weekly mean pain severity VAS score, regardless of discontinuation from study treatment discontinuations for any reason, and regardless of occasional use of rescue medication or prohibited medications?

The supplementary analysis to the primary analysis will be performed on the FAS population. The supplementary analysis will be performed using all observed data regardless of intercurrent events (a treatment policy strategy). The target population, the primary variable and the summary measure of the supplementary estimand for the supplementary estimand are the same as for the primary estimand. Differently from the primary estimand, this analysis considers all intercurrent events are inherent in the treatment regimen and will not exclude any observed data even when subjects take rescue/prohibited medications or discontinue treatment.

For subjects who use rescue medications for pain relief due to any reason, all observed data will be used for analysis. If not available, missing data will be under the MAR assumption for both SAF312 and placebo arms.

For subjects who take the following prohibited medications:

- Ocular, nasal, inhaled, or systemic corticosteroids
- Use of oral or topical ocular antihistamines, mast cell stabilizers

All observed data will be used for analysis. If not available, missing data on the day(s) +3 days of the IEs will be under the MAR assumption for both SAF312 arms and placebo arm.

For subjects with new use or change in dosing of neuromodulators for any reason or topical ocular NGF, all observed data will be used for analysis. If not available, missing data on the days of IEs will be under the MAR assumption for both SAF312 and placebo arms.

For subjects who discontinue from study treatment due to any reason, retrieved drop-out (RDO) data collected after study treatment discontinuation will be used for analysis. If not available, missing data after treatment discontinuation will be multiply imputed based on Jump to Reference assumption for SAF312 arms and under the MAR assumption for placebo arm.

The supplementary analysis will be performed using MMRM but includes all the observed data and imputed data if appropriate.

Subgroup analysis

Subgroup analyses of the primary endpoints will be outlined in the statistical analysis plan (SAP).

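### The protocol does not secure the daily pain diary after treatment discontinuation, so the treatment-policy analysis may have few retrieved data for discontinuers

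*Protocol*

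**What the plan says.** **Analysis.** Protocol 12.4.6 asks for the effect regardless of treatment discontinuation. For subjects who stop, "retrieved drop-out (RDO) data collected after study treatment discontinuation will be used for analysis". Only where such data are missing does it impute, by Jump to Reference (J2R) in the SAF312 arms and under MAR in the placebo arm. The endpoint is a weekly mean of daily eDiary scores (Protocol 12.4.1).

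**Conduct after a stop.** Protocol 9.1.1 says: "Subjects who discontinue from study treatment agree to return for the end of treatment and follow-up visits indicated in the Assessment Schedule". It then gives a minimum: "After discontinuation from study treatment, at a minimum, in abbreviated visits, the following data should be collected at clinic visits or via telephone/email contact". The list is "New / concomitant treatments" and AE/SAE.

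**Diary.** Table 8-1, footnote 4, has sites remind subjects to make the entry before the evening dose, "every day until the evening prior to the EOT visit". The row "Collect electronic diary" is marked at Visit 6/EOT only.

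**Timing of EOT.** Protocol section 3 says "End of Treatment (EOT) will occur at Visit 6 when the subject receives the last study treatment", and Table 8-1 puts Visit 6 at Day 84 ± 2.

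**Glossary.** For a subject who discontinues study treatment: "Participant agrees to the other protocol required assessments including follow-up".

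**SAP.** In Table 2-4 the discontinuation row imputes the weekly means from the week of the stop onwards and does not mention retrieved data. The other rows state that all observed data are used. SAP section 4 declares no change to the protocol-specified analyses.

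**The concern.** The analysis section relies on pain scores after a treatment stop, but no conduct section clearly tells a site to obtain them. A site could hold an early EOT visit for a subject who stops at Week 5, take the diary back and still comply with 9.1.1 and Table 8-1. No pain score would exist after that visit.

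This analysis is the plan's only alternative to the hypothetical handling of discontinuation. The primary estimand excludes data after the stop (Protocol 12.4.3), and sensitivity analyses are declared not applicable (12.4.5). Reasons for stopping listed in 9.1.1 include adverse events and unsatisfactory effect. For those subjects an assumed course of pain is a weak substitute for an observed one. If few are observed, their contribution reflects the imputation rule.

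**Working it through.** **1. Where diary entry ends, under each reading of EOT**

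| Reading | Text in favour | Consequence for a Week 5 discontinuer |
|---|---|---|
| EOT is brought forward | Section 3 links EOT to the last study treatment; SAP 2.1.1.3 defines the end-of-treatment date by the last study treatment; 9.1.1 names only the EOT and follow-up visits | Diary ends and the device is returned at the early visit; no score afterwards |
| EOT stays at Day 84 | Table 8-1 fixes Visit 6 at Day 84 ± 2; the glossary has discontinuers agree to other required assessments | Diary can run to Day 84, but 9.1.1 does not list it among the minimum data |

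The prompt final visit in Protocol section 8 is for subjects who leave the study, so it does not settle the question for those who only stop treatment. Under either reading the daily VAS is not expressly required after the stop.

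**2. The plan's own power figure**

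Inputs from Protocol 12.8.1: difference 15 mm, SD 23 mm, 50 per arm, two-sided 5% adjusted for two comparisons.

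Non-centrality = 15 / (23 × √(2/50)) = 15 / 4.6 = 3.26. With α = 0.025 and 98 degrees of freedom, the noncentral t gives 83.6%. The normal approximation gives 84.6%. The stated 83% is reproduced, so 15 mm and 50 per arm can serve as the reference case.

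**3. Share of Week 12 values imputed**

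Let d be the share of an arm off treatment before Week 12, and r the share of those with a retrieved Week 12 value that is used. The documents give neither. The nearest figure is the optional increase to 60 per arm, which would keep 50 at a loss of 1 − 50/60 = 16.7%.

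Imputed share = d(1 − r), ignoring other missing data.

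| d (assumed) | Discontinuers per 50 | r = 0 | r = 0.5 | r = 1 |
|---|---|---|---|---|
| 10% | 5 | 10% | 5% | 0% |
| 20% | 10 | 20% | 10% | 0% |
| 30% | 15 | 30% | 15% | 0% |

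Even at r = 0, 70–90% of Week 12 values are observed.

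**4. What J2R does to the estimate with no retrieval**

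Approximation: SAF312 discontinuers take the placebo mean at Week 12, and MAR leaves the placebo mean unchanged. Expected effect = 15 × (1 − d).

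- d = 10%: 15 × 0.9 = 13.5 mm
- d = 20%: 15 × 0.8 = 12.0 mm
- d = 30%: 15 × 0.7 = 10.5 mm

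**5. How to read that shift**

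Suppose SAF312 discontinuers in truth keep a fraction b of the 15 mm at Week 12. Full retrieval would then estimate 15 × (1 − d(1 − b)), and the gap to J2R is 15 × d × b. With b = 0 the gap is zero. With b = 1 it is 15 × 0.1 = 1.5 mm to 15 × 0.3 = 4.5 mm. If discontinuers do worse than placebo, b is negative and J2R is the more favourable figure. The documents give no value of b; retrieved diary data would inform it.

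**The case against.** The strongest reply is that nothing in the protocol stops the diary when treatment stops. The 9.1.1 list is explicitly a minimum for site contacts, whereas the diary is done at home. The glossary has discontinuers agree to the other required assessments, and Protocol 12.4.3 and 12.4.6 both presuppose data after the stop. Section 6.7.1.1 asks for study drug back when treatment is discontinued, and there is no matching instruction for the diary. The reference to the evening dose can be read as fixing the time of day, since Protocol 8.3.1 also requires an evening entry in the undosed observation period.

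Much of this stands. A reader might infer that pain data are not collected after a stop, or that retrieved data will hardly exist. The documents support neither; they leave the matter open. A reader might also infer that the treatment-policy question cannot be answered from observed data. That goes too far: only discontinuers' post-stop weeks are imputed, and data under rescue or prohibited medication are used as observed.

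What does not stand is that the glossary closes the gap. It refers to required assessments, and the schedule ends the diary at an EOT visit whose timing for discontinuers is undefined. The analysis sections presuppose data without instructing any site to obtain them.

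It is also fair to say that collecting the diary would not by itself change the result while SAP Table 2-4 imputes those weeks. The text of SAP 5.2.2 is not visible in the copy reviewed, so nothing is inferred from it.

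**Conclusion.** The point holds as a gap in what is required. Protocol 9.1.1 does not require the daily pain severity VAS after treatment discontinuation, and the timing of EOT for discontinuers is not stated. The retrieved data that 12.4.6 uses first may therefore be sparse, and may differ by site. Discontinuers' post-stop weeks may then rest largely on J2R or MAR imputation.

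The size is illustrative only. At an assumed 10–30% discontinuation with no retrieval, 15 mm becomes 13.5–10.5 mm under J2R. It is tempting to call the difference of 1.5–4.5 mm a bias, but it measures J2R against full retained benefit, which patients off treatment may not have. Nor could all of the 5–15 discontinuers per arm be retrieved, because some will also leave the study.

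The primary analysis is unaffected. This is a worthwhile, inexpensive improvement to a supplementary analysis in a Phase 2 trial.

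**What to change.** 1. **Protocol 9.1.1:** add to the minimum data after a treatment stop *daily pain severity VAS by eDiary through Day 84, for subjects who remain in the study*.
2. **Table 8-1 and footnote 4:** state that the evening entry continues when no dose is taken, and that the eDiary is collected at Day 84 or at withdrawal from the study.
3. **SAP Table 2-4:** reconcile the discontinuation row with Protocol 12.4.6, so that observed weekly means after discontinuation are used and only missing ones are imputed.

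Items 1 and 2 supply the data and item 3 lets them count, so all three are needed. The cost is wording and an eDiary setting. Subjects already hold the device and no visits are added. The downside is a few more weeks of diary burden for subjects who stopped treatment. Diary days that are missed cannot be recovered later.
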